11. DATA COLLECTION AND MANAGEMENT

11.1 Data Collection and Management

11.1.1 Fitbit Data Collection

Each participant will be given a Fitbit device at the time of study enrollment. A de-identified Fitbit account will be created for all users, which will then be the account from which the data will be retrieved, maintaining individual patient privacy without PHI. The account username and passwords associated with their device will be de-identified. A log of the de-identified account usernames with the participant ID number will be kept in a password-protected file and stored on the research hard drive.

With appropriate consent in place, the research-allocated Fitbit device will be registered on the Fitbit Application Programming Interface (API) on the Fitbit developer site to enable scripted, automated data collection of pre-defined data elements to be collected on the study. The de-identified data of all patients will be stored and evaluated in real-time by the research team using a platform called PittBit. PittBit is a web-based application that creates a dashboard of the synced Fitbit data from participants, including active minutes, steps, and heart rate data. Each Fitbit de-identified account will be canceled and, therefore, unregistered from the API at the end of an individual participant's follow-up period so that no additional data from the Fitbit can be accessed after the study window. The participant will be able to keep their Fitbit after completing the study.

11.1.2 Storage and Future Use

Fitbit data collected on the PittBit application are de-identified. They will be limited to patient active minutes, steps, and heart rate from enrollment to the end of the follow-up time period, after which the Fitbit account created for study purposes will be canceled and unenrolled from the API. Hence, no further data collection is possible. Clinical data will be recorded in a limited dataset that will be maintained for the life of the study. The patient name will be omitted, but MRN will be retained until the dataset is completed and removed from the final dataset. Data will be maintained in a password-protected spreadsheet on the research drive, with only study team members granted access.

11.1.3 Retention/Access

Only designated research team members and the Principal Investigator will have access to PitBitt, the dataset, and the password. The data on PittBit is fully de-identified, and the study dataset will not be transferred or shared with any external institutions without amendment to this protocol and required approvals (institutional and by law). The quality management Program within the ISCI will maintain oversite of this study. The data fields retained will be listed in 11.1.4.

11.1.4 Data Fields

Data will be retrieved from:

- Fitbit Device
- EPIC
- Aria
- Raystation
- Patient web-based surveys using REDCap (or paper surveys or interview if patient preference)

Data to be collected include:

- From medical chart:
 - o Variables in data tracker sheet (Appendix 12)
- FitBit Active minutes, steps, heart rate and last sync, using PittBit data platform
- Patient self-report: REDCap web-based surveys (or paper surveys or interview if patient preference) per protocol
- Subjective notes from exit interview

11.2 Security

The study is registered and approved by the Fitbit company and will be performed in compliance with both Fitbit regulations and the Inova IRB.

All personnel involved with this project are trained on the use and protection of patient information as required by Inova.

All personnel involved with study activities and/or data will have completed appropriate training in patient privacy and human subjects regulations.

A backup of the dataset will be stored as a password-protected file on [name] office computer, which remains locked when she is not directly accessing it. A backup will be retained every three months.

11.2.1 Anonymization, De-Identification and/or Destruction

Fitbit logins and passwords will be anonymous for each participant. A code will be generated for all data collected once the dataset has been validated to replace participant identifiers and maintained only by the PI and delegated research team. Fitbit data collected on the PittBit application are de-identified and will be limited to patient active minutes, steps, and heart rate from enrollment to the end of follow-up time period. Each individual Fitbit de-identified account will be cancelled and therefore unregistered from the API at the end of an individual participant's follow-up period so that no additional data from the Fitbit can be accessed after the study window. The participant will be able to keep their Fitbit after completing the study.

All data will be saved under password protection with password access granted only to the PI and critical research team members.

11.3 Release of Locally Banked Data

Not applicable.

11.4 Confidentiality

All data and records generated during this study will be kept confidential in accordance with Inova Health System institutional policies and HIPAA on participant privacy. The Investigator and other site personnel will not use such data and records for any purpose other than conducting the study.

No identifiable data will be used for future use without first obtaining IRB approval or determination of exemption. The investigator will obtain a data use agreement between the provider of the data and any recipient researchers through the Office of Research, Business Office, before sharing a limited dataset.

All data will be kept confidential. Fitbit data collected on the PittBit application are de-identified and will be limited to patient active minutes, steps, and heart rate from enrollment to the end of follow-up time period. The study data will be stored on the research drive using password protection, which will only be accessed by the research team. When dataset is verified, the PHI will be removed and replaced with a code/participant ID that will remain in a separate password protected file.

11.4.1 Certificate of Confidentiality

Not applicable.

12. DATA ANALYTICS

12.1 Study Objectives

Primary:

The primary objective of this study is to evaluate the feasibility of conducting a randomized trial of an exercise coaching program to encourage physical activity for women treated with adjuvant pelvic intensity-modulated radiation therapy treatment for endometrial cancer.

Secondary:

- 1) To collect initial efficacy evaluation of the exercise coaching program on patient-reported fatigue, bowel/urinary toxicity, QoL, cognitive function, sexual function and satisfaction, and self-efficacy, as well as distance walked during 6MWT between the immediate and delayed-start group from baseline to pre-specified time points (end of RT, 5-7 weeks post RT, and 16-19 weeks post RT) to guide statistical planning for follow-up study.
- 2) To measure the prevalence of fatigue at baseline in the population of endometrial cancer patients recommended pelvic radiation therapy using data collected in the screening process.
- 3) To explore potential behavioral mechanisms (mediators) and variables that influence the strength of the intervention effect (moderators).

12.2 Analytics

This study will enroll 16 patients. At the Inova Schar Cancer Institute Fairfax location, approximately 24 patients will undergo a course of pelvic radiation per year. Additionally, approximately 24 patients will undergo a course of pelvic radiation per year across Inova Loudoun, Inova Alexandria, and Inova Fair Oaks Hospitals. With the goal of the study to evaluate adherence to and the acceptability and feasibility of the intervention as part of a pilot study, the sample size was determined with the goal of completing accrual of the study within one year, accruing across all four sites.

Primary Objective Analytical Plan

Feasibility of conducting a randomized trial of this nature will be evaluated on the basis of process feasibility and resources and data-management feasibility.

The *process* feasibility will be evaluated on:

- 1) Recruitment acceptability from the provider and patient perspective:
 - a. Provider acceptability of the intervention will be defined as the proportion of patients identified on pre-screening by the PI that the primary clinician agrees of patient suitability for offering enrollment on the trial and proceeding to completion of screening steps if patient is interested in the study. We set an a priori goal of 50% provider acceptability.
 - b. Patient acceptability of the intervention will be defined as the proportion

of patients who agreed to consent and then proceed to completion of screening steps. We set an a priori goal of 50% patient acceptability.

- 2) Appropriateness of the screening criteria:
 - a. Screening criteria appropriateness will be defined as the proportion of patients who are screened who proceeded to allocation of intervention groups. We set an a priori goal of 50% of appropriateness of the screening criteria.
- 3) Adherence to the exercise coaching session intervention:
 - a. Individual adherence to coaching sessions will be defined as complete adherence when engaging in 10 of the 10 planned exercise coaching sessions and high adherence as engaging in at least 7 of the planned 10 exercise coach check-ins. We set an a priori goal of overall 70% participant adherence to the coaching sessions, to be analyzed per cohort (6 of 8 participants in each arm demonstrating high adherence as defined above).
- 4) Adherence to the physical activity monitor usage to track steps and active minutes:
 - a. Individual adherence to the physical activity monitor will be defined as wearing the activity tracker for at least 8 hours a day for 70% of the days in the study. Heart rate will be used to determine wear-time. We set an a priori goal of overall 70% participant adherence to the physical activity monitor, to be analyzed per cohort (6 of 8 participants in each arm demonstrating adherence as defined above).
- 5) Adherence to recommendation of 150 minutes per week of moderate physical activity:
 - a. Individual adherence to regular physical activity will be defined as meeting the recommendation of 150 minutes of moderate physical activity per week, based on the Physical Activity Guidelines for Americans developed by the U.S. Department of Health and Human Services (HHS). The target for participant adherence is set at an a priori goal of 70%.

The *resource and management* feasibility will be assessed based on the capacity of the exercise coach and research team to perform the required tasks of the protocol:

- 1) Adherence to the timeline of study procedures and human and data management issues that could potentially arise during a full-scale RCT will be tracked. Adherence to the study timeline for completion of required patient surveys and 6MWT as well as appropriate scheduling (patient attendance not required) of the exercise coaching sessions and follow-ups will be a proxy measurement of research resource and human data management acceptability. We set an a priori goal of 80% adherence.

Secondary Objective Analytical Plan

- 1) Changes in patient-reported fatigue, bowel/urinary toxicity, QoL, cognitive function, sexual function and satisfaction, and self-efficacy, as well as distance walked during 6MWT from baseline to pre-specified time points (end of RT, 5-7 weeks post RT, and 16-19 weeks post RT) within and between each group will be compared using two-sample t-test or Wilcoxon Rank Sum test when appropriate. Repeated measure models/linear mixed effect models may also be used to explore the changes in self-reported questionnaires over time among different treatment groups. Data will be analyzed based on the intention-to-treat principle and used to estimate treatment effect size for future trial design.
- 2) Prevalence of fatigue at baseline in the population of endometrial cancer patients receiving pelvic radiation therapy will be reported using data collected in the screening process.
- 3) Exploratory analysis of potential behavioral mechanisms (mediators) and variables that influence the strength of the intervention effect (moderators) will be performed.

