7. PARTICIPANT SELECTION

7.1 Eligibility Criteria

Inclusion Criteria:

- At least 18 years of age
- Pathologic diagnosis of endometrial cancer (any histology, Stage I-IVA)
- Has undergone modified radical or radical hysterectomy
- Plan to receive adjuvant treatment with pelvic external beam radiation therapy at ISCI
- ECOG performance status of 0-1
- Patient has a computer, smart phone, or tablet for virtual access to the web-based platform and email
- Able to read, understand and provide written informed consent
- Deemed appropriate for unmonitored exercise by treating physician based on the following evidence-based criteria (1)
 - Walk without any assistance or assistance device
 - Absence of significant cognitive impairment
 - Absence of high risk for falls
- Participant does not need to refrain from any activity

Exclusion Criteria:

- Unable to schedule and attend coaching visits
- Participation in a regular exercise program of ≥ 150 minutes of moderate intensity exercise a week at baseline
- Unable to perform the five-times stand test
- Medical comorbidities including:
 - Unstable angina
 - Uncontrolled dysrhythmias
 - Acute pulmonary embolus
 - Active pulmonary infection

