8. RECRUITMENT METHODS

8.1 Methods

8.1.1 Recruitment

Eligible patients will be pre-screened by PI on a weekly basis, who will then email the primary radiation oncologist. The primary radiation oncologist will determine if the intervention is acceptable to offer to the

potential patient at the time of consultation, and this will inform the provider acceptability ratio, one of the primary outcomes of the study. The primary radiation oncologist will discuss the study with the patient at the time of consultation and, if the patient is interested, will notify the research team to facilitate consent for enrollment.

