8.1.2 Screening

Participants will be screened to review inclusion and exclusion criteria (see Appendix 2).

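### Provider acceptability (item 1a) can count a physician's finding that a woman is unfit for unmonitored exercise, which is an inclusion criterion, as a provider refusal

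*Protocol*

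**What the plan says.** Protocol 12.2, item 1a, and the matching synopsis text define provider acceptability of the intervention as the "proportion of patients identified on pre-screening by the PI that the primary clinician agrees of patient suitability for offering enrollment on the trial". The same sentence adds that the woman then goes on to complete screening if she is interested. The target is explicit: "We set an a priori goal of 50% provider acceptability".

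Section 8.1.1 describes how the ratio arises. First, "Eligible patients will be pre-screened by PI on a weekly basis, who will then email the primary radiation oncologist". The oncologist then decides at consultation whether the intervention is acceptable to offer, and "this will inform the provider acceptability ratio, one of the primary outcomes of the study".

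Section 7.1 lists as an inclusion criterion "Deemed appropriate for unmonitored exercise by treating physician based on the following evidence-based criteria". Three items sit under it: walking unaided, no significant cognitive impairment, and no high fall risk.

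Formal eligibility review comes later. Under 8.1.2, "Participants will be screened to review inclusion and exclusion criteria", and 9.1 and Table 1 place this at the screening visit together with consent. Section 8.1.2.1 limits screen failures to women who have consented. Item 2 of 12.2 (appropriateness of the screening criteria) is the share of screened women who reach allocation, also with a 50% goal.

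**The concern.** One yes or no from the clinician, given before consent, can carry two different judgements. One is whether the woman meets a criterion that the protocol assigns to the physician. The other is whether the physician is willing to offer the trial. Item 1a divides the yes answers by all pre-screened women and does not separate the reasons for a no.

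A physician who declines because a woman needs help to walk is applying 7.1 correctly, yet the woman counts against acceptability of the intervention. She never reaches screening, so she is absent from item 2, the measure meant to show whether the criteria are too strict. One primary measure is pulled down, and the other misses what it exists to capture.

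The pilot is meant to guide the design of a follow-up trial. Low acceptability caused by reluctant providers calls for work with providers. Low acceptability caused by physician-judged fitness raises a question about the criteria or the population. The ratio as defined does not tell these apart.

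**Working it through.** The 50% goal is set and not derived, so there is no figure to reproduce. The check first traces where a refusal is counted and then asks how far the ratio can move.

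**Where a woman is counted**

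| Point at which she is lost | Lowers item 1a? | Seen by item 2? |
|---|---|---|
| Ineligibility noticed at the PI's pre-screen | No, never in the denominator | No |
| Physician finds her unfit at consultation, before consent | Yes | No |
| Physician finds her fit but declines to offer the trial | Yes | No |
| Found ineligible at screening, after consent | No | Yes |

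Item 1a treats the second and third rows alike.

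**Inputs**

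- Goal: 50% (12.2, item 1a).
- u: share of pre-screened women whom the clinician declines as unfit. Not in the protocol; assumed.
- w: share of fit women to whom the clinician agrees to offer the trial. Not in the protocol; assumed.
- N: at most 24 + 24 = 48 pelvic radiation courses a year across the four sites (12.2). This is an upper bound on one year's pre-screened pool.

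**Formulas**

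- Measured ratio as defined: N(1 - u)w / N = (1 - u)w.
- Ratio without women declined as unfit: N(1 - u)w / N(1 - u) = w.
- Willingness needed for the measured ratio to reach the goal: w = 0.50 / (1 - u).

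**Results**

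| u (assumed) | Measured ratio at w = 70% | Measured ratio at w = 80% | w needed to reach 50% |
|---|---|---|---|
| 0% | 70% | 80% | 50.0% |
| 10% | 63% | 72% | 55.6% |
| 20% | 56% | 64% | 62.5% |
| 30% | 49% | 56% | 71.4% |
| 40% | 42% | 48% | 83.3% |
| 50% | 35% | 40% | 100% |

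For u = 30% and w = 70% the measured ratio is 0.70 × 0.70 = 0.49. With N = 48, the binomial chance of reaching at least 24 of 48 at that rate is 0.50. With only the fit women in the denominator (48 × 0.70 = 33.6, taken as 34), the chance of reaching 50% at w = 70% is 0.996.

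**Direction.** Since 1 - u cannot exceed 1, the measured ratio cannot exceed w. In expectation the mixing can only make the goal look harder to reach.

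**The case against.** Several points can be made in the protocol's favour.

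- *Eligibility review comes later.* Item 1a puts completion of screening after the clinician's agreement, and 8.1.2, 9.1 and Table 1 put the criteria review at screening. Fitness could be judged there and scored under item 2. This stands in part: some fitness failures may surface only after consent. But 7.1 gives the judgement to the treating physician, 8.1.1 asks the oncologist at consultation whether the intervention is acceptable to offer, and nothing tells that clinician to set fitness aside.
- *The denominator is already filtered.* The PI pre-screens before the oncologist is emailed. This stands. A reader might infer that all ineligibility is scored against providers. The text supports only physician-judged fitness, plus anything the pre-screen missed.
- *Not every activity criterion belongs to the physician.* The requirement that the participant need not refrain from any activity is a separate bullet in 7.1. Only walking, cognition and fall risk sit under the physician's judgement.
- *Suitability is what item 1a says it measures.* The share of pre-screened women found suitable is a legitimate recruitment figure. This stands, and it is a reason to keep the ratio. The protocol, however, labels it provider acceptability of the intervention, and suitability alone does not carry that meaning.
- *Removing unfit women from the denominator has its own bias.* The same clinician would decide who leaves it, and a reluctant clinician who cites fall risk would raise the ratio. This stands, and it argues against replacing the stated denominator.
- *Reasons may be logged in appendices that are not shown.* That is possible, but item 1a as written makes no use of them.

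**Conclusion.** The point holds in a limited form. Item 1a mixes a physician-assigned inclusion criterion with willingness to offer the trial, and women declined as unfit before consent are invisible to item 2. The measured ratio is (1 - u)w. The distortion is downward only and of unknown size, because neither u nor w can be taken from the protocol. The 49% is an illustration, not an expected result.

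A reader might go further and infer that the 50% goal could easily be missed even if every clinician supported the trial. The protocol does not support that. With w = 100% the ratio is 1 - u, so the expected ratio falls below 50% only if more than half of the pre-screened women are unfit. At u = 30% full support gives 70%. Nothing in the protocol points to more than half, and 7.1 already requires ECOG 0-1. The realistic harm is a borderline or low figure that cannot be interpreted. Nor does the text show that the wrong remedy would follow, since no go/no-go rule is attached to the goal.

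The conclusion assumes that the primary clinician, the primary radiation oncologist and the treating physician are the same role. The wording suggests this but does not say it. It also assumes that at least some fitness judgements are made at the consultation.

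**What to change.** In 12.2 item 1a and the synopsis:

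1. Have the clinician record one reason for each refusal when it is made: a named 7.1 item, or other.
2. Keep the stated ratio over all pre-screened women.
3. Report beside it, against the same 50% goal, the ratio that excludes women declined for a named 7.1 item.
4. Count the excluded women separately as eligibility losses and present them alongside item 2.

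The cost is about one sentence in each place and a tick-box in the clinician's reply to the PI. The reason is hard to reconstruct later, so it should be in place from the start of pre-screening.

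The drawback is that the same clinician assigns the reason. If every reluctant refusal were labelled as a named item, the second ratio would be 100% whatever w is, while the stated ratio would stay at (1 - u)w. That is why both are reported. If unfit women are always labelled as such and mislabelling runs only from reluctance to unfitness, the stated ratio is a lower bound for willingness and the second an upper bound.

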The integration of exercise therapy is recommended for cancer patients and survivors to mitigate the side effects of therapy and the risk of recurrence. Cancer patients, however, often experience barriers to meeting the recommended guidelines. It is well documented that at least two-thirds of cancer patients are unable to adhere to the recommendation of exercise due to symptoms and barriers, with women being more likely than men to report barriers to adherence to exercise. Patients with low adherence report higher symptom burden including pain and fatigue. Radiation treatment, with usually a daily treatment schedule, poses additional barriers to engaging in routine exercise and there is a large gap in data to guide the incorporation of exercise therapy into the treatment of patients receiving radiation given these unique challenges. The available data is limited largely to men with prostate cancer, which reports improvement in a number of symptoms with exercise during treatment.

The most common gynecologic malignancy in the United States is endometrial cancer, and the incidence continues to rise. Many women with endometrial cancer will be recommended to undergo pelvic radiation therapy to reduce recurrence risks. For women undergoing pelvic radiation therapy, fatigue-limiting activities of daily living (ADLs) is a common acute side effect of therapy. Although it is accepted that exercise helps treatment-related fatigue in the general cancer population, *patient-specific factors* (more advanced age, post-operative status, and the prevalence of baseline obesity and co-morbidities) and *treatment-specific factors* (daily radiation for 5 weeks, often concurrent chemotherapy) pose significant challenges with the feasibility of endometrial cancer patients to engage in exercise.

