6. STUDY TIMELINE

6.1 Individual Participation

The study duration per participant will be up to six months. Patients will be requested to wear their Fitbit from the start of enrollment to the 16-19 weeks post RT visit, participating in standard-of-care weekly visits during RT at 5-7 weeks post RT, and again 16-19 weeks post RT. The ten consecutive weekly exercise coaching check-in sessions will start for the early intervention during the first week of RT and the delayed intervention at 6-8 weeks post RT.

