6.2.2 Follow-up

Follow-up will continue for up to 19 weeks after completion of pelvic RT.

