9.3.4 Week 5 of pelvic RT (Fraction 21-25)

Items to be completed at week 5 of RT:

- Fitbit data will be collected on all patients.
- The following assessments are collected:

- FACIT-F
- EPIC Bowel and Urinary short form assessments
- PROMIS-29 QoL metric
- PROMIS Cognitive Function
- PROMIS Self-Efficacy for Chronic Conditions
- 6MWT

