9.5 Non-compliance and Lost to Follow-Up

The following actions must be taken if a participant fails to return to the clinic for a required study visit:

- 9.5.1 The adherence to the Fitbit will be routinely monitored during exercise check-ins or during the active-monitoring check-ins and data will be recorded for analysis using the PittBit dashboard. Email reminders may be sent to participants who are found not to be wearing their Fitbit as instructed (see Appendix 6).
- 9.5.2 For missed visits, the site will attempt to contact the participant and reschedule the missed visit and discuss with the participant the importance of maintaining the assigned visit schedule and ascertain if the participant wishes to and/or should continue in the study.
- 9.5.3 Before a participant is deemed lost to follow-up, the investigator or designee will make every effort to regain contact with the participant (where possible, 3 telephone calls and, if necessary, a certified letter to the participant's last known mailing address or local equivalent methods). These contact attempts should be documented in the participant's medical record or study file.
- 9.5.4 Should the participant continue to be unreachable, he/she/they will be considered to have withdrawn from the study with a primary reason of lost to follow-up.
- 9.5.5 Definition of Non-compliance: A patient will be considered non-compliant to the exercise coaching intervention arm if they fail to engage in 70% of the weekly check-ins. A patient will be considered non-compliant to the

physical activity monitor if they do not wear the Fitbit activity tracker for at least 8 hours a day for 70% of the days in the study. As this is a pilot study, patients will not be removed from study due to non-compliance, as the primary outcome is to evaluate adherence.

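### The Fitbit-wear criterion is one 70% share over all study days, so it can be met with little or no wear during radiation

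*Protocol*

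**What the plan says.** Section 12.2 (Primary Objective Analytical Plan, item 4) defines individual adherence to the activity monitor as "wearing the activity tracker for at least 8 hours a day for 70% of the days in the study". Heart rate determines wear time. The goal is 70% of participants, judged per arm as "6 of 8 participants in each arm demonstrating adherence as defined above". The synopsis repeats this. Section 9.5.5 uses the same whole-study share to define non-compliance with the device.

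The days counted are set by section 6.1: "Patients will be requested to wear their Fitbit from the start of enrollment to the 16-19 weeks post RT visit". Section 6.2.2 adds: "Follow-up will continue for up to 19 weeks after completion of pelvic RT". The abstract and synopsis describe the treatment as "daily radiation for 5 weeks, often concurrent chemotherapy" and name it among the factors that make exercise hard for these patients.

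No section sets a minimum for the radiation weeks, the coaching weeks or any other part of follow-up.

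**The concern.** The pilot asks whether a trial of exercise coaching can be run in women receiving pelvic radiation, and the protocol singles out daily radiation as the special barrier. Whether the device can be worn in those weeks is thus a central feasibility question. A share pooled over five to six months lets good wear after treatment offset poor wear during it.

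Contact also differs between arms and then swaps. During radiation the immediate arm has weekly coaching and the delayed arm a call of about five minutes every two weeks (9.3.7, 9.3.8). After the 5-7-week visit this reverses. If wear follows contact, the arms could differ in each period and still show similar pooled rates.

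At stake is what a pass on a primary criterion means. An arm could meet its goal while the radiation weeks hold few usable step and active-minute data. Criterion 5 (150 minutes a week) would suffer too, if it is scored from device minutes.

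**Working it through.** **The plan's own figure.** 70% of 8 is 5.6, rounded up to 6, which is 75%. The 6-of-8 goal reproduces.

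**Inputs**
- Radiation: 25 fractions over 5 weeks (Table 1, 9.3.3, 9.3.4), taken as 5 × 7 = 35 calendar days. From a Monday start to the Friday of week 5 it is 33.
- Follow-up after radiation: 16 to 19 weeks, or 112 to 133 days (6.1, 6.2.2).
- Wear days before radiation: not stated, so 0 to 14 are assumed. The documents differ on when the count starts: simulation in Table 1, enrollment in 6.1, handing over of the device in 9.3.1.2. More days here only lower the share taken by radiation. The longest case, 14 + 35 + 133 = 182 days, agrees with section 6.1: "The study duration per participant will be up to six months".

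**Formulas.** T = days before + days of radiation + days after. Days needed = 0.70 × T, rounded up. Days that may be missed = T − days needed. Wear required on other days, with none during radiation = days needed ÷ (T − radiation days).

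With 35 days of radiation:

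| Before | After | T | Needed | May be missed | Radiation share of T | Required on other days |
|---|---|---|---|---|---|---|
| 0 | 112 | 147 | 103 | 44 | 23.8% | 103/112 = 92.0% |
| 0 | 133 | 168 | 118 | 50 | 20.8% | 118/133 = 88.7% |
| 14 | 112 | 161 | 113 | 48 | 21.7% | 113/126 = 89.7% |
| 14 | 133 | 182 | 128 | 54 | 19.2% | 128/147 = 87.1% |

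No wear during radiation can pass in every row, with 44 − 35 = 9 to 54 − 35 = 19 missed days to spare. With 33 days of radiation, 14 before and 133 after, T is 180, 126 days are needed, and 126/147 = 85.7% is required on the other days. The range across all variants is thus about 86-92%.

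**Sensitivity.** The result reverses only if T falls below 35 ÷ 0.30 ≈ 117 days, which a completer cannot reach. If radiation ran to 45 days, its share with 112 days after would be 45/157 = 28.7%, still under 30%.

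**A less extreme case.** Take wear on 10 of 35 radiation days and about 85% of days afterwards, with no days before radiation:
- 16 weeks after: (10 + 95)/147 = 71.4%.
- 19 weeks after: (10 + 113)/168 = 73.2%.

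She is adherent with 25 of 35 radiation days (71%) missing.

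**Arm level.** If all six adherent women lack wear during radiation and the other two do as well, the arm still meets 6 of 8.

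**Where the rule does bite**
- Missing a full 70-day coaching block leaves (T − 70)/T, which is 75/145 = 52% to 112/182 = 62%, and fails.
- No wear from the first fraction to the 5-7-week visit is 35 + 35 = 70 to 35 + 49 = 84 days, against 44 to 54 allowed, and also fails.

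**The case against.** The extreme case is unlikely. During radiation the coach reviews Fitbit data weekly in the immediate arm (5.1.3), the coordinator asks the delayed arm about wear and syncing every two weeks (9.3.8), the dashboard shows data in real time (11.1.1), and e-mail reminders are possible (9.5.1). For an arm to pass with no radiation data, six women would have to skip all of radiation and then wear the device about nine days in ten. This stands as a reason to expect something milder, but monitoring does not change the definition, and the 10-of-35 case needs no such behaviour.

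A whole-study summary is also a legitimate choice for a 16-patient pilot, the rule is stated consistently, and period breakdowns are often left to the analysis plan. What answers this is that the protocol itself fixes the criterion as an a priori primary measure. Choosing periods after the data are seen would weaken it.

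Three stronger readings are tempting and not supported:
- A reader might infer that the criterion can pass with no data from the whole coaching or comparison period. It cannot: those gaps exceed the allowance.
- A reader might infer that only the time up to the 5-7-week visit matters, so the criterion should be restricted to it. The arms also differ afterwards, in reverse, and between-group comparison at 16-19 weeks is planned. Restriction would drop the delayed arm's coaching from the criterion. It would also still let 21 to 25 radiation days be missed (30% of 70 to 84 days).
- A reader might infer that the follow-up trial would rest on device outcomes. The protocol does not say so: the between-group outcomes in 12.2 are questionnaires and the walk test.

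**Conclusion.** The point holds in a limited form. Criterion 4 can be met with little or no device wear during radiation, because the 44 to 54 days that may be missed exceed the roughly 35 days of treatment. Meeting 6 of 8 therefore does not by itself show that activity can be tracked during radiation. It does show that device data were not absent throughout a coaching block for the women counted as adherent.

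The conclusion rests on 5 weeks of radiation, full follow-up to 16-19 weeks, and an assumed 0 to 2 weeks of wear beforehand. It is not sensitive to these within the schedule the protocol allows. The trial's validity is not in question. The weakness lies in what one primary feasibility result can be taken to mean, and it is worth correcting before data are examined.

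**What to change.** Keep the whole-study criterion as it stands: 8 hours, 70% of days, 6 of 8 per arm. Add to section 12.2 and the synopsis that the same rule is also scored per arm, from the same data, in three periods:
- (a) first to last fraction, where 70% means 25 of 35 days (24 of 33);
- (b) end of radiation to the 5-7-week visit;
- (c) the 5-7-week visit to the 16-19-week visit.

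State that device tracking will be called feasible during radiation only if 6 of 8 women in each arm reach 70% in (a). Keep (c) in the criterion, since it holds the delayed arm's coaching.

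The cost is a few sentences in two places and a few lines in the wear-time program. Daily device data are already collected, so nothing is added for participants. There are two drawbacks. The reported adherence may look less favourable, and estimates by period are imprecise: with 8 women per arm, one woman moves the rate by 1/8, or 12.5 percentage points.
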